### 6.3. Visit Windows

Data analyzed by-visit-analysis (including efficacy, laboratory data, visit sign, and ECG) will be summarized by the study scheduled visits described in the study protocol and SAP, "Schedule of Event". The analysis visit windows will be exhaustive so that all available values obtained from unscheduled visits, early termination (ET) visit and end of treatment (EOT)/end of study (EOS) have the potential to be summarized. No analysis visit windows will be applied for the study scheduled visits.

The following analysis visit windows will be used to map the unscheduled visits, ET and EOT/EOS visits, based on the study day:

Visit	Target Day	Analysis Time Window Based on Study day*
Screening	<1	<1
Baseline	1	1
Week 1	8	[2,11]
Week 2	15	[12,18]
Week 3	22	[19,25]
Week 4	29	[26, 32]
Week 5	36	[33, 39]
Week 6	43	[40, 46]
Week 7	50	[47, 53]
Week 8	57	[54, 64]
Week 10	71	[65, 81]
Week 13	92	[82, 102]
Week 16	113	[103, 116]
Week 17	120	[117, 130]
Week 20	141	[131, 155]
Week 24	169	>=156

\*Study day is calculated relative to the date of first study drug injection.

In general, the following order will be used to select the record for analysis at given visit:

1. Scheduled visit
2. Early termination (ET) or end of study (EOS), whichever comes first if scheduled visit not available
3. Unscheduled visit if both scheduled visit and ET/EOT/EOS are not available

For the multiple measurements of the same test in the same window, the following rules will be used to pick up the analysis value:

- If multiple valid values of a variable within an analysis visit window, the closest from the target study day will be selected.
- If the difference is a tie, the value after the targeted study day will be used.
- If multiple available values of a variable exist within a same day, then the first value of the day will be selected.

#### **6.4. Unscheduled Assessments**

Both scheduled and unscheduled measurements will be considered for determining abnormal/PCSV values from laboratory, vital sign or ECG as well as the baseline values.

## 7. INTERIM ANALYSIS

There is no interim analysis.

## **8. SOFTWARE**

All analyses will be done using SAS Version 9.4 or above.

## 10. APPENDIX

### 10.1. Summary of Statistical Analyses

#### Efficacy Analysis:

Parameter(s)	Endpoints	Primary Statistical Method	Supportive/Sensitivity Statistical Method	Subgroup Analysis
TNSS	percent change and absolute change from baseline in AUC for TNSS (0-1 hr post peak TNSS) at week 17	ANCOVA model, missing data imputed by Multiple Imputation (MI)	Yes	Yes
TOSS	percent change and absolute change from baseline in AUC for TOSS (0-1 hr post peak TNSS) at week 17	ANCOVA model, missing data imputed by Multiple Imputation (MI)	No	No
Skin Prick Test with Serial Allergen Titration	percent change and absolute change from baseline in AUC for wheal sizes (diameter) (0-1 hr post peak TNSS) at week 17	ANCOVA model, missing data imputed by Multiple Imputation (MI)	No	No
skin Timothy Grass intradermal injection	percent change and absolute change from baseline in wheal size (diameter) induced by skin Timothy Grass intradermal injection 6 hrs after the challenge) at week 17	ANCOVA model, missing data imputed by Multiple Imputation (MI)	No	No

Parameter(s)	Endpoints	Primary Statistical Method	Supportive/Sensitivity Statistical Method	Subgroup Analysis
PNIF	percent change and absolute change from baseline in PNIF AUC (0-1 hr post peak TNSS, and 1-6hr post peak TNSS) at week 17	ANCOVA model, missing data imputed by Multiple Imputation (MI)	No	No
sneeze count	percent change and absolute change from baseline in sneeze count AUC (0-1 hr post peak TNSS, and 1-6hr post peak TNSS) at week 17	ANCOVA model, missing data imputed by Multiple Imputation (MI)	No	No

**Safety Analyses:**

Endpoint	Analysis Populations	Statistical Method	Supportive Analysis	Subgroup Analysis	Other Analyses
Adverse Events	SAF	Descriptive statistics	No	Yes for selected AE summary	No
Laboratory Measures	SAF	Descriptive Statistics	No	No	No
Vital sign	SAF	Descriptive Statistics	No	No	No
ECG	SAF	Descriptive Statistics	No	No	No

## 10.2. Schedule of Time and Events

### Schedule of Events – Screening, Baseline and Treatment Periods

Study Procedure	Screening Period				Treatment Period															EO T	NA C	Unschedu led Visit (if applicabl e) 	EO S	V1 8	E T
	V 1	V 2	NA C	R  V 4	V 5	V 6	V 7	V8	V9	V1 0	V1 1	V1 2	V1 3	V1 4	V1 5	V1 6	V1 7								
Week (W)				1	2	3	4	5	6	7	8	10	13	16	17	20				24					
Study Day	+1 to -84			1	8	1 5	22	29	36	43	50	57	71	92	11 3	120	14 1			169					
Window in Weeks	±1			-1	± 1	± 1	±1	±1	±1	±1	±1	±1	±1	±1	±1	±1	±1			±3  8					
Screening/Baseline																									
Inclusion/Exclusion	X	X	X	X																					
Informed Consent	X																								
	X																								
Medical History	X																								

Study Procedure	Screening Period		Treatment Period															EO T NA C V1 6	Unscheduled Visit (if applicable) 	EO S V1 8	E T
	V 1	V 2	NA C V3	R  V 4	V 5	V 6	V 7	V8	V9	V1 0	V1 1	V1 2	V1 3	V1 4	V1 5	V1 6	V1 7				
Week (W)				1	2	3	4	5	6	7	8	10	13	16	17	20			24		
Study Day	+1 to -84	1	8	1 5	22	29	36	43	50	57	71	92	11 3	120	14 1			169			
Window in Weeks	±1			-1 1	± 1	± 1	±1	±1	±1	±1	±1	±1	±1	±1	±1	±1	±1	±3  8			
Demographics	X																				
Randomization (R)				X																	
SPT for Timothy Grass	X																				
Serum Timothy Grass sIgE	X																				
Treatment:																					
Dupilumab/ PBO loading 				X																	
Dupilumab 300 mg q 2 weeks dosing 					X	□□-----X----- -----□											X				
Visit for SCIT Injections 				X	X 5	X	X 	X	X 	X	X	X 	X	X 	X	X 		X			
Premedicate with loratadine 10 mg orally 				X	X	X	X	X	X	X	X	X	X	X	X	X		X			

Study Procedure	Screening Period		Treatment Period															EO T NA C V1 6	Unsched uled Visit (if applicabl e) 	EO S V1 8	E T
	V 1	V 2	NA C V3	R  V 4	V 5	V 6	V 7	V8	V9	V1 0	V1 1	V1 2	V1 3	V1 4	V1 5	V1 6	V1 7				
Week (W)				1	2	3	4	5	6	7	8	10	13	16	17	20			24		
Study Day	+1 to -84		1	8	1 5	22	29	36	43	50	57	71	92	11 3	120	14 1			169		
Window in Weeks	±1			-1	± 1	± 1	±1	±1	±1	±1	±1	±1	±1	±1	±1	±1			±3  8		
Training for Self-injection (dupilumab/PB O)				X																	
Dupilumab/PB O distribution				X		X						X		X				X			
Dupilumab/PB O diary review/ Accountability 																		X		X	
Subject Dosing Diary 				X		X		X		X		X	X	X				X		X	
Concomitant Meds	X	X	X	X	X	X	X	X	X	X	X	X	X	X	X	X	X	X	X	X	
Efficacy:																					
TNSS		X	X													X		X		X	
TOSS			X														X			X	
PNIF			X														X			X	

Study Procedure	Screening Period		Treatment Period															EO T NA C V1 6 V1 7	Unscheduled Visit (if applicable) 	EO S V1 8	E T
	V 1	V 2	NA C V3	R  V 4	V 5	V 6	V 7	V8	V9	V1 0	V1 1	V1 2	V1 3	V1 4	V1 5	V1 6	V1 7				
Week (W)				1	2	3	4	5	6	7	8	10	13	16	17	20		24			
Study Day	+1 to -84		1	8	1 5	22	29	36	43	50	57	71	92	11 3	120	14 1		169			
Window in Weeks	±1			-1	± 1	± 1	±1	±1	±1	±1	±1	±1	±1	±1	±1	±1		±3  8			
Intradermal skin challenge testing (LPR)			X														X			X	
Skin Prick Test with Serial Allergen Titration (EPR)			X														X			X	
Safety:																					
Weight	X		X														X		X		X
Height	X																				
Vital Signs	X		X	X	X	X	X	X	X	X	X	X	X	X	X	X	X	X	X	X	
Physical Examination	X		X														X		X	X	X
Spirometry		X																X			
ECG		X															X		X	X	X
Peak expiratory flow 		X	X														X		X		
Adverse events	X	X	X	X	X	X	X	X	X	X	X	X	X	X	X	X	X	X	X	X	

Study Procedure	Screening Period		Treatment Period															EO T NA C V1 6 V1 7	Unscheduled Visit (if applicable) 	EO S V1 8	E T
	V 1	V 2	NA C V3	R  V 4	V 5	V 6	V 7	V8	V9	V1 0	V1 1	V1 2	V1 3	V1 4	V1 5	V1 6	V1 7				
Week (W)				1	2	3	4	5	6	7	8	10	13	16	17	20			24		
Study Day	+1 to -84	1	8	1 5	22	29	36	43	50	57	71	92	11 3	120	14 1			169			
Window in Weeks	±1			-1 1	± 1	± 1	±1	±1	±1	±1	±1	±1	±1	±1	±1	±1	±1	±3  8			
Laboratory Testing																					
HIV Ab, HBsAg, HBcAb, Hep C Ab,		X																X			
Hematology, Chemistry		X						X			X		X		X	X	X	X	X	X	
Urinalysis		X						X			X		X		X	X	X	X	X	X	
Pregnancy Test if indicated [in WOCBP]		X  4		X  5			X  5			X  5		X  5		X 	X  5	X 	X 	X  4			
Nasal mucosal brushing 		X  6	X									X  7		X					X		
Nasal fluid collection			X											X					X		

Study Procedure	Screening Period		Treatment Period															EO T NA C V1 6	Unscheduled Visit (if applicable) 	EO S V1 8	E T
	V 1	V 2	NA C V3	R  V 4	V 5	V 6	V 7	V8	V9	V1 0	V1 1	V1 2	V1 3	V1 4	V1 5	V1 6	V1 7				
Week (W)				1	2	3	4	5	6	7	8	10	13	16	17	20		24			
Study Day	+1 to -84	1	8	1 5	22	29	36	43	50	57	71	92	11 3	120	14 1		169				
Window in Weeks	±1		-1	± 1	± 1	±1	±1	±1	±1	±1	±1	±1	±1	±1	±1	±1	±3  8				
Future Biomedical Research:																					
Research serum 			X	X		X		X		X		X		X		X		X	X		
Research plasma 			X	X		X		X		X		X		X		X		X	X		
			X																		
Biomarker:																					
Blood for basophil sensitivity assays, Th2A profiling and PBMC banking 			X													X			X		

Study Procedure	Screening Period		Treatment Period															EO T NA C V1 6	Unscheduled Visit (if applicable) 	EO S V1 8	E T
	V 1	V 2	NA C V3	R  V 4	V 5	V 6	V 7	V8	V9	V1 0	V1 1	V1 2	V1 3	V1 4	V1 5	V1 6	V1 7				
Week (W)				1	2	3	4	5	6	7	8	10	13	16	17	20		24			
Study Day	+1 to -84	1	8	1 5	22	29	36	43	50	57	71	92	11 3	120	14 1		169				
Window in Weeks	±1			-1 ± 1	± 1	±1	±1	±1	±1	±1	±1	±1	±1	±1	±1	±1	±3  8				
SerumTARC 		X	X					X				X		X		X	X	X	X	X	
Serum total IgE 		X	X		X		X		X		X		X		X	X		X	X		
Serum Timothy Grass sIgE 		X	X		X		X		X		X		X		X	X		X	X		
Serum Timothy Grass sIgG4 		X	X		X		X		X		X		X		X	X		X	X		
Drug Concentration and ADA:																					

Study Procedure	Screening Period		R 	Treatment Period														EO T	NA C	Unscheduled Visit (if applicable) 	EO S	V1 8	E T
	V 1	V 2		NA C	V 4	V 5	V 6	V 7	V8	V9	V1 0	V1 1	V1 2	V1 3	V1 4	V1 5	V1 6	V1 7					
Week (W)				1	2	3	4	5	6	7	8	10	13	16	17	20			24				
Study Day	+1 to -84	1	8	1 5	22	29	36	43	50	57	71	92	11 3	120	14 1			169					
Window in Weeks	±1		-1	± 1	± 1	±1	±1	±1	±1	±1	±1	±1	±1	±1	±1	±1		±3  8					
Functional dupilumab PK 		X							X		X		X		X	X			X	X			
Anti-drug antibody  (ADA)		X														X			X	X			

### Footnotes for the Schedule of Events Table

1. Randomization (V4) must occur within 2 weeks of NAC (V3)
2. Dupilumab or placebo for dupilumab loading dose is given day of randomization. Subsequent dupilumab/placebo dosing is given Q2W.
3. Dupilumab/placebo dosing must be given  $\pm 3$  days of the visit window.
4. SCIT/placebo should be given 1 to 7 days following dupilumab/placebo loading dose. Subsequent SCIT/placebo dosing follows dosing regimen as depicted in [Table 2](#).
5. During week 2, week 4, week 6, week 10, and week 16, when both dupilumab/placebo and SCIT/placebo are given in the same week, SCIT/placebo and dupilumab/placebo are NOT to be given on the same day (can be 1 day to 7 days apart) AND SCIT/placebo and dupilumab/placebo are to be given in a different anatomical location.
6. For SCIT/placebo visits, subjects are to be premedicated with an antihistamine as described in the protocol Section 5.1.1.2
7. Starting at visit 4, study drug will be dispensed to the subject for the dose that will be administered before the next dupilumab/placebo distribution visit. Subjects will return the original kit box at each dupilumab/placebo distribution visit for accountability
8. For subjects who choose to self-administer study drug, counsel subject on proper dosing diary completion/reporting of each dose of study drug that is administered outside of the study site
9. Peak expiratory flow will be measured prior to NAC in any subject with a history of asthma. Peak expiratory flow must be  $>80\%$  predicted to perform the NAC in any subject with a history of asthma (please refer to the peak flow meter chart in the Study Operations Manual as a reference of predicted peak expiratory flow values)
10. Collected 6 hours post NAC
11. Collected pre-NAC
12. Serum samples to be collected for ADA and PK assessments, prior to dosing of dupilumab at timepoints indicated in the Schedule of events
13. Assessments and procedures at the unscheduled visit are to be performed at the discretion of the principal investigator
14. Serum pregnancy test
15. Urine pregnancy test
16. Baseline nasal brushing and nasal brushing on study drug (which is performed at least 28 days before the final NAC) will not be performed if they interfere with the subject's timely completion of the study (prior to the onset of the subsequent allergy season) as outlined in the Study Operations Manual
17. Should be performed approximately 28 days before the final NAC
18. The visit should be conducted as close as possible to the designated study schedule date and the window for the days used only as needed.

### 10.3. Analyses of Efficacy Variables Criteria for Potentially Clinically Significant Values (PCSV) for Adult Patients

Parameter	Treatment Emergent PCSV	Comments
Clinical Chemistry		
ALT*	
 
>3 and <math>\leq</math> 5 ULN and baseline <math>\leq</math> 3 ULN*
 
>5 and <math>\leq</math> 10 ULN and baseline <math>\leq</math> 5 ULN
 
>10 and <math>\leq</math> 20 ULN and baseline <math>\leq</math> 10 ULN
 
>20 ULN and baseline <math>\leq</math> 20 ULN
 
	
 
Enzyme activity must be expressed in ULN, not in IU/L.
 
Concept paper on DILI – FDA draft Guidance Oct 2007.
 
Each category is calculated independently.
 
* At least one level is required, multiple levels are optional for phase 2/3 studies. If it is desirable to get the distribution across the different PCSV levels, additional shift table on <math>\leq</math>3, >3 to <math>\leq</math>5, >5 to <math>\leq</math>10, >10 to <math>\leq</math>20, and > 20 category for baseline vs. post baseline may be provided
 

AST*	
 
>3 and <math>\leq</math> 5 ULN and baseline <math>\leq</math> 3 ULN*
 
>5 and <math>\leq</math> 10 ULN and baseline <math>\leq</math> 5 ULN
 
>10 and <math>\leq</math> 20 ULN and baseline <math>\leq</math> 10 ULN
 
>20 ULN and baseline <math>\leq</math> 20 ULN
 
	
 
Enzyme activity must be expressed in ULN, not in IU/L.
 
Concept paper on DILI – FDA draft Guidance Oct 2007.
 
Each category is calculated independently.
 
* At least one level is required, multiple levels are optional for phase 2/3 studies. If it is desirable to get the distribution across the different PCSV levels, additional shift table on <math>\leq</math>3, >3 to <math>\leq</math>5, >5 to <math>\leq</math>10, >10 to <math>\leq</math>20, and > 20 category for baseline vs. post baseline may be provided
 

Alkaline Phosphatase	>1.5 ULN and baseline $\leq$ 1.5 ULN	
 
Enzyme activity must be expressed in ULN, not in IU/L.
 
Concept paper on DILI – FDA draft Guidance Oct 2007.
 

Parameter	Treatment Emergent PCSV	Comments
Total Bilirubin*	>1.5 and $\leq$ 2 ULN and baseline $\leq$ 1.5 ULN*  >2 ULN and baseline $\leq$ 2.0 ULN	Must be expressed in ULN, not in $\mu$ mol/L or mg/L. Categories are cumulative.  Concept paper on DILI – FDA draft Guidance Oct 2007.  * At least one level is required, multiple levels are optional for phase 2/3 studies. If it is desirable to get the distribution of significant level, additional shift table on $\leq$ 1.5, >1.5 to $\leq$ 2.0 and > 2.0 category for baseline vs. post baseline may be provided
Conjugated Bilirubin	(Direct Bilirubin $>$ 35% Total Bilirubin and Total Bilirubin $>$ 1.5 ULN) and (Direct Bilirubin $\leq$ =35% Total Bilirubin or Total Bilirubin $\leq$ =1.5 ULN) at baseline	Conjugated bilirubin dosed on a case-by-case basis.
ALT and Total Bilirubin	(ALT $>$ 3 ULN and TBILI $>$ 2 ULN) and baseline (ALT $\leq$ =3 ULN or TBILI $\leq$ =2 ULN)	Concept paper on DILI – FDA draft Guidance Oct 2007.
CPK*	>3 and $\leq$ 10 ULN and baseline $\leq$ 3ULN*  >10 ULN and baseline $\leq$ 10ULN	FDA Feb 2005.  Am J Cardiol April 2006.  Categories are cumulative.  * At least one level is required, multiple levels are optional for phase 2/3 studies. If it is desirable to get the distribution of significant level, additional shift table on $\leq$ 3, >3 to $\leq$ 10, and > 10 category for baseline vs. post baseline may be provided
Creatinine	$\geq$ 150 $\mu$ mol/L (Adults) and baseline $<$ 150 $\mu$ mol/L  $\geq$ =30% change from baseline and $<$ 100% change from baseline  $\geq$ 100% change from baseline	Benichou C., 1994.  3 independent criteria

Parameter	Treatment Emergent PCSV	Comments
Uric Acid		Harrison- Principles of internal Medicine 17 th Ed., 2008.
Hyperuricemia	>408 µmol/L and <=408 µmol/L at baseline	
Hypouricemia	<120 µmol/L and >= 120 µmol/L at baseline	Two independent criteria
Blood Urea Nitrogen	≥17 mmol/L and <17 mmol/L at baseline	Two independent criteria
Chloride		Two independent criteria
Hypochloremia	<80 mmol/L and baseline ≥ 80	
Hyperchloremia	mmol/L >115 mmol/L and baseline ≤ 115 mmol/L	
Sodium		Two independent criteria
Hyponatremia	≤129 mmol/L and baseline > 129	
Hypernatremia	mmol/L ≥160 mmol/L and baseline <160 mmol/L	
Potassium		FDA Feb 2005.
Hypokalemia	<3 mmol/L and baseline ≥ 3 mmol/L	Two independent criteria
Hyperkalemia	≥5.5 mmol/L and baseline <5.5 mmol/L	
Total Cholesterol	≥7.74 mmol/L and < 7.74 mmol/L at baseline	Threshold for therapeutic intervention.
Triglycerides	≥4.6 mmol/L and < 4.6 mmol/L at baseline	Threshold for therapeutic intervention.
Glucose		
Hypoglycaemia	(≤3.9 mmol/L and <LLN) and (>3.9 mmol/L or >=LLN) at baseline	ADA May 2005.
Hyperglycaemia	≥11.1 mmol/L (unfasted); ≥7 mmol/L (fasted) and < 11.1 mmol/L (unfasted); <7 mmol/L (fasted) at baseline	ADA Jan 2008.
HbA1c	>8% and <= 8% at baseline	
Albumin	≤25 g/L and >25 g/L at baseline	

Parameter	Treatment Emergent PCSV	Comments
CRP	>2 ULN or >10 mg/L (if ULN not provided) and <=2 ULN or <=10 mg/L (if ULN not provided) at baseline	FDA Sept 2005.
Hematology		
WBC	<3.0 Giga/L and >=3.0 Giga/L at baseline (Non-Black); <2.0 Giga/L and >=2.0 Giga/L at baseline (Black) ≥16.0 Giga/L and < 16 Giga/L at baseline	Increase in WBC: not relevant.  To be interpreted only if no differential count available.
Lymphocytes	>4.0 Giga/L and <= 4.0 Giga/L at baseline	
Neutrophils	<1.5 Giga/L and >=1.5 Giga/L at baseline (Non-Black); <1.0 Giga/L and >=1.0 Giga/L at baseline (Black)	International Consensus meeting on drug-induced blood cytopenias, 1991. FDA criteria.
Monocytes	>0.7 Giga/L <= 0.7 Giga/L at baseline	
Basophils	>0.1 Giga/L <= 0.1 Giga/L at baseline	
Eosinophils	(>0.5 Giga/L and >ULN) and (<=0.5 Giga/L or <= ULN at baseline)	Harrison- Principles of internal Medicine 17 th Ed., 2008.
Hemoglobin	≤115 g/L and > 115 g/L at baseline for male; ≤95 g/L and > 95 g/L at baseline for Female.  ≥185 g/L and <185 g/L at baseline for Male; ≥165 g/L and < 165 g/L at baseline for Female	Three criteria are independent.  Criteria based upon decrease from baseline are more relevant than based on absolute value. Other categories for decrease from baseline can be used (≥30 g/L, ≥40 g/L, ≥50 g/L).
Decrease from Baseline ≥20 g/L		

Parameter	Treatment Emergent PCSV	Comments
Hematocrit	$\leq 0.37$ v/v and $> 0.37$ v/v at baseline for Male ; $\leq 0.32$ v/v and $> 0.32$ v/v at baseline for Female $\geq 0.55$ v/v and $< 0.55$ v/v at baseline for Male ; $\geq 0.5$ v/v and $< 0.5$ v/v at baseline for Female	Two Criteria are independent
RBC	Female $< 3$ Tera/L and baseline $\geq 3$ Tera/L $\geq 6$ Tera/L and baseline $< 6$ Tera/L Male $< 4$ Tera/L and baseline $\geq 4$ Tera/L $\geq 7$ Tera/L and baseline $< 7$ Tera/L	Unless specifically required for particular drug development, the analysis is redundant with that of Hb. Otherwise, consider FDA criteria.
Platelets	$< 100$ Giga/L and $\geq 100$ Giga/L at baseline $\geq 700$ Giga/L and $< 700$ Giga/L at baseline	International Consensus meeting on drug-induced blood cytopenias, 1991. Two independent criteria
Urinalysis		
pH	$\leq 4.6$ and $> 4.6$ at baseline $\geq 8$ and $< 8$ at baseline	Two independent criteria
Vital signs		
HR	$\leq 50$ bpm and decrease from baseline $\geq 20$ bpm $\geq 120$ bpm and increase from baseline $\geq 20$ bpm	To be applied for all positions (including missing) except STANDING.
SBP	$\leq 95$ mmHg and decrease from baseline $\geq 20$ mmHg $\geq 160$ mmHg and increase from baseline $\geq 20$ mmHg	To be applied for all positions (including missing) except STANDING.
DBP	$\leq 45$ mmHg and decrease from baseline $\geq 10$ mmHg $\geq 110$ mmHg and increase from baseline $\geq 10$ mmHg	To be applied for all positions (including missing) except STANDING.

Parameter	Treatment Emergent PCSV	Comments
Weight	$\geq 5\%$ increase from baseline $\geq 5\%$ decrease from baseline	FDA Feb 2007.
ECG		Ref.: CPMP 1997 guideline.
HR	$\leq 50$ bpm and decrease from baseline $\geq 20$ bpm $\geq 120$ bpm and increase from baseline $\geq 20$ bpm	
PR	$\geq 220$ ms and increase from baseline $\geq 20$ ms	
QRS	$\geq 120$ ms & $< 120$ ms at baseline	
QTc	Absolute values (ms)	To be applied to any kind of QT correction formula.
Borderline	Borderline:	
Prolonged*	431-450 ms and $< 431$ ms at baseline	
Additional	for Male; 451-470 ms and $< 451$ ms at baseline for Female	
	Prolonged: $>450$ to $<500$ ms and $\leq 450$ ms at baseline for Male; $>470$ to $<500$ ms and $\leq 470$ ms at baseline for Female $\geq 500$ ms and $< 500$ ms at baseline	*QTc prolonged and $\Delta QTc > 60$ ms are the PCSA to be identified in individual subjects/patients listings.
		5 independent criteria
Increase from baseline		
	Borderline: Increase from baseline 30-60 ms	
	Prolonged: Increase from baseline $> 60$ ms	

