### 7.3.3. Reasons for Permanent Discontinuation of Study Drug (Dupilumab or Placebo for Dupilumab and SCIT or Placebo for SCIT)

Subjects will be permanently discontinued from study treatment in the event of:

- Anaphylactic reaction to study drug (dupilumab or placebo for dupilumab and SCIT or placebo for SCIT)
- Evidence of pregnancy
- Any infection that:
  - Requires parenteral treatment with antibiotic, antifungal, antiviral, anti-parasitic, or anti-protozoal agent
  - Requires oral treatment with such agents for longer than 2 weeks
  - Is opportunistic, such as tuberculosis and other infections whose nature or course may suggest an immunocompromised status
- Severe laboratory abnormalities, such as:
  - Neutrophil count  $\leq 0.5 \times 10^3/\mu\text{L}$
  - Platelet count  $\leq 50 \times 10^3/\mu\text{L}$ 
    - ALT and/or aspartate aminotransferase (AST) values  $>3 \times \text{ULN}$  with total bilirubin  $>2 \times \text{ULN}$ , excluding confirmed Gilbert's Syndrome
  - Confirmed AST and/or ALT  $>5 \times \text{ULN}$  (for more than 2 weeks)
- Other reasons that may lead to the permanent discontinuation of study treatment include:
  - Certain AEs deemed related to the study drug (dupilumab or placebo for dupilumab and SCIT or placebo for SCIT) (eg, severe and prolonged ISRs) or study procedures

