### **5.8.3. Clinical Laboratory Measurements**

Laboratory measurements include clinical chemistry, hematology and urinalysis results, and will be converted to standard international units. Summaries of laboratory variables will include:

- Descriptive statistics of laboratory result and change from baseline by visit
- The number (n) and percentage (%) of patients with abnormal lab value during study whose baseline values are normal (overall and per each lab parameter)
- The number (n) and percentage (%) of patients with treatment-emergent PCSVs
- Shift tables based on baseline normal/abnormal and other tabular and graphical methods may be used to present the results for parameters of interest

Listing of all laboratory parameters normal range, abnormal flag and treatment-emergent PCSV by patient and visit will be provided.

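### On the minimum that SAP 10.3 requires, an ALT or AST value above 5 x ULN can escape the PCSV count; the bilirubin and CPK rows contradict themselves, and AST-led cases never enter the combined liver row

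*SAP*

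**What the plan says.** SAP 5.8.3 commits to the number and "percentage (%) of patients with treatment-emergent PCSVs", using the thresholds in SAP 10.3. Protocol 10.4.4.2 promises a PCSV count for each laboratory test. The relevant rows of SAP 10.3 are:

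- **ALT and AST.** Four levels: above 3 to 5 (starred), above 5 to 10, above 10 to 20, and above 20 x ULN, each with its own baseline condition. The comment says "Each category is calculated independently".
- **Total bilirubin.** Above 1.5 to 2 x ULN (starred) and above 2 x ULN.
- **CPK.** Above 3 to 10 x ULN (starred) and above 10 x ULN.
- **Note on all four parameters.** "At least one level is required, multiple levels are optional for phase 2/3 studies". A shift table across levels is discretionary: "category for baseline vs. post baseline may be provided".
- **Comment on bilirubin and CPK only.** "Categories are cumulative".
- **Combined row, "ALT and Total Bilirubin".** ALT above 3 x ULN with total bilirubin above 2 x ULN. It has no upper cap, and AST does not appear.

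Protocol 7.3.3 lists two liver criteria for permanent discontinuation. The first is "ALT and/or aspartate aminotransferase (AST) values" above 3 x ULN with total bilirubin above 2 x ULN, excluding confirmed Gilbert's syndrome. The second is confirmed AST and/or ALT above 5 x ULN lasting more than 2 weeks. Protocol 7.3.3.1 names CPK above 10 x ULN among the reasons for which dosing may be suspended temporarily.

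**The concern.** A PCSV table is where a reader looks for the number of subjects per arm who crossed a threshold. A band closed at the top does not give that number, because a subject with a worse value drops out of it. If the bands above are optional, the more severe result can go uncounted while the milder one is counted.

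There are two further problems. A capped band cannot also be cumulative, so two programmers following the bilirubin or CPK row could produce different counts from the same data. And the combined row cannot be read against the protocol's criterion, because it omits one of the two enzymes that the criterion names. At stake is the arm-level count of liver and CPK abnormalities, not any efficacy result.

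**Working it through.** The plan gives no figure to reproduce, so the check applies the written rules to constructed cases.

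**Inputs.** Bands, notes and the combined row are from SAP 10.3; the criteria are from Protocol 7.3.3 and 7.3.3.1. The patient values are assumptions, in multiples of ULN with normal baseline, chosen to resemble cases that those criteria address. Values not shown lie below every band.

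**Readings.**
- A: only the starred level is reported, with its cap.
- B: as A, but bilirubin and CPK are read as cumulative, so their caps are ignored.
- C: every listed level is reported.

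**Rule.** A subject is in a capped level if lower limit < value ≤ upper limit. The combined row needs ALT > 3 and bilirubin > 2. For example, ALT 6 fails 3 < 6 ≤ 5. AST 8 with ALT 2.5 and bilirubin 2.5 fails the AST band (8 > 5), the capped bilirubin band (2.5 > 2) and the combined row (ALT 2.5 ≤ 3).

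| Case (x ULN) | A | B | C | In combined row? |
|---|---|---|---|---|
| ALT 6, sustained | none | none | ALT | not applicable |
| AST 6, sustained | none | none | AST | not applicable |
| ALT 4, bilirubin 2.5 | ALT, combined | ALT, bilirubin, combined | ALT, bilirubin, combined | yes |
| ALT 8, bilirubin 2.5 | combined | bilirubin, combined | ALT, bilirubin, combined | yes |
| AST 4, ALT 2.5, bilirubin 2.5 | AST | AST, bilirubin | AST, bilirubin | never |
| AST 8, ALT 2.5, bilirubin 2.5 | none | bilirubin | AST, bilirubin | never |
| CPK 12 | none | CPK | CPK | not applicable |

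**Results.**
- In no PCSV count: 4 of 7 under A, 2 of 7 under B, 0 of 7 under C.
- Combined row: 2 of the 4 cases with bilirubin above 2 x ULN, on every reading. The two missed are the AST-led ones.
- The ALT/AST gap does not depend on the starred level being the one reported. The three lower levels are capped and the fourth starts above 20 x ULN, so no single level counts everyone above 3, or everyone above 5 x ULN.
- One subject in a planned arm of 25 is 1/25 = 4 percentage points.

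The seven cases show which patterns are lost. They are not an estimate of how often those patterns occur.

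**The case against.** A reader might infer that these subjects vanish from the safety tables. They do not. SAP 5.8.3 requires by-visit descriptive statistics (which include the maximum), a count per parameter of subjects newly abnormal from a normal baseline, and a full listing by patient and visit. A discontinuation reported as a TEAE is tabulated under SAP 5.8.1. That part of the objection stands, and the point is confined to the PCSV counts. The other outputs are not substitutes, however: none counts subjects above a stated multiple of ULN, and the PCSV flag in the listing depends on the same definitions.

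It also stands that the SAP nowhere says only the starred level will be reported. SAP 10.3 lists all levels as treatment-emergent PCSVs, and reporting all of them loses no case from the single-parameter counts. But the note expressly permits less, and a plan meant to pre-specify should not leave that open.

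Four other tempting readings go too far:
- **CPK above 10 and bilirubin above 2 x ULN are dropped.** The word cumulative would bring both into the lower level. What the text shows is a contradiction, not a clear omission. The CPK provision is also a discretionary temporary suspension.
- **A single ALT spike, say 12 x ULN and normal at the next sample, is a missed stopping case.** Protocol 7.3.3 asks for a confirmed elevation lasting more than 2 weeks, which one spike does not show.
- **Combined cases in general are missed.** ALT-led cases are fully caught by the uncapped combined row.
- **Sparse sampling makes skipping the band likely.** Chemistry is scheduled at weeks 4, 8, 13, 17, 20 and 24, significantly abnormal results must be repeated (Protocol 8.2.2.6), and unscheduled values count (SAP 6.4). A repeat may fall inside the band, so omission is possible rather than expected.

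Finally, nothing obliges PCSV thresholds to mirror discontinuation rules; the neutrophil and platelet rows do not. That is fair, but those rows are open on the severe side, so a worse value still counts.

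**Conclusion.** The point holds as a defect in how the counts are defined, and it has three parts of differing strength.

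1. **AST absent from the combined row: certain on every reading.** A subject with AST above 3, ALT at or below 3 and bilirubin above 2 x ULN meets the numerical part of the Protocol 7.3.3 criterion and is never in the combined count.
2. **Capped ALT/AST level: conditional.** A subject whose only raised value exceeds 5 x ULN is missing from that enzyme's PCSV count if the sponsor reports just the starred level, as the note allows, and no other sample falls in the band.
3. **Bilirubin and CPK: an internal contradiction.** The count depends on whether the caps or the comment is programmed.

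Each affected subject moves an arm of 25 by 4 percentage points. The documents give no event rate from which to say how many there would be. Subjects remain visible in other laboratory outputs, so this is a reporting correction worth making before database lock, not a threat to the trial's safety monitoring.

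**What to change.** Amend SAP 10.3 as follows; the clinical rules stay as they are.

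- **ALT and AST, each:** mandatory levels of above 3 x ULN with baseline at or below 3, and above 5 x ULN with baseline at or below 5, both open-ended. The higher bands can stay as extra detail. Reword the comment on independent calculation to say that these levels overlap.
- **Total bilirubin:** remove the cap on the lower level so that it agrees with cumulative (above 1.5 x ULN, baseline at or below 1.5), and always report above 2 x ULN.
- **CPK:** likewise, above 3 x ULN (baseline at or below 3), and always report above 10 x ULN.
- **Combined row:** (ALT or AST) above 3 x ULN with total bilirubin above 2 x ULN. The matching baseline condition is that both ALT and AST are at or below 3 x ULN, or bilirubin is at or below 2 x ULN. Flag confirmed Gilbert's cases so that the row can be read against Protocol 7.3.3.
- **Note on levels:** replace the required/optional wording with the list of levels that will be reported.

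Under these definitions all seven constructed cases are counted, and all four with bilirubin above 2 x ULN fall in the combined row. The above-5 level will include values that do not meet the confirmed, more-than-2-weeks condition. No PCSV row captures that duration, and a footnote should say so.

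The cost is revised table wording and a few more output rows. No new data are needed.
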